2.3. Secondary Aim

2.3.1. Collect preliminary data on RCC patients' symptoms, health care utilization, quality of life, distress level and oral drug adherence while on targeted therapy or immunotherapy.

- To determine how patients' treatment-related toxicities correlate to their quality of life, distress level, drug adherence and health care utilization.

3.0.CHARACTERISTICS OF THE RESEARCH POPULATION

3.1 Number of Subjects: We expect to recruit 50 advanced renal cell carcinoma patients from the genitourinary oncology program at Wilmot Cancer Institute of the University of Rochester Medical Center over a one-year period.

3.2 Gender of Subjects: Both men and women will be enrolled in this study. Advanced RCC is known to be almost twice as prevalent in men than women [24], therefore we can expect a roughly 2:1 male to female enrollment rate.

3.3 Age of Subjects: We will recruit patients 18 years and older for this study, however RCC is very uncommon in patients <45 years of age and typically affects adults between the ages of 45 and 84 [1].

3.4 Racial and Ethnic Origin: This study has no enrollment restrictions based upon race or ethnic origin. RCC is known to be less prevalent in Asian and Pacific Islanders [1].

3.5 Inclusion Criteria:

- 3.5.1 Diagnosis of histologically confirmed renal cell carcinoma of any subtype with either pathological or radiographic evidence of metastatic disease
- 3.5.2 Greater than 18 years of age
- 3.5.3 A participating Wilmot Cancer Center oncologist has determined that candidate should be started on either oral targeted therapy or immunotherapy for treatment of their advanced RCC; this can be for first-line or any subsequent line therapy**
- 3.5.4 Able to provide written informed consent
- 3.5.5 Proficient in the English language and self-reports as literate
- 3.5.6 Must have an active email address or access to a smart device

3.6 Exclusion Criteria:

- 3.6.1 Women cannot be breast-feeding
- 3.6.2 Does not have regular access to the internet
- 3.6.3 Unable to come to the Wilmot Cancer Center for appointments every 3-4 months for routine visits with their primary oncologist
- 3.6.4 Subjects who were on the study previously will not be allowed to re-enroll in the event of a treatment change

3.7 Vulnerable Subjects: No special classes of subjects such as fetuses, neonates, children, pregnant women, prisoners, institutionalized individuals or other vulnerable populations will be recruited.

4.0.SUBJECT IDENTIFICATION, RECRUITMENT, AND CONSENT

4.1 Identification and Recruitment

The study coordinator and investigators will review active patient records to identify all patients who meet eligibility criteria. Potential subjects will be approached for interest at their next scheduled visit with their genitourinary oncologist at the Wilmot Cancer Center. After identification of potential subjects for the study, Drs. [name] (PI), [name] and [name], who are medical oncologists at the Wilmot Cancer Institute, will introduce the study to potentially eligible subjects.

4.2 Consent Process

For eligible subjects who are interested in study participation, a study team member will walk the subject through the consent form to ensure comprehension and the subject will be given the option to sign the consent form. The study team member will be available to answer any questions that the subjects may have about the study prior to consenting and throughout the entire study period. If the subject opts not to participate in the study, we will record their reason in a screening log which will not be connected to any identifying patient information.

5.0. REGISTRATION

5.1 Registration Procedures

To enroll a subject who meets the eligibility criteria (see sections 3.5 and 3.6) and who has signed the informed consent documents, log on to the *Research Electronic Data Capture (REDCap)* and enter the subject information as outlined below:

- A subject ID number will be assigned in sequential order as the subjects are enrolled into the study. The 2-digit number will be used to identify the subject on all study forms.
- First and last initials
- Birth date (MM/DD/YYYY)
- Gender
- Race
- Nine-digit zip code

6.0. METHODS AND STUDY PROCEDURES

6.1 Overview of Study:

We will conduct a phase II, single-arm clinical trial to assess the feasibility of reporting and managing side effects from oral targeted therapy or immunotherapy, through Carevive software, in patients who have advanced RCC. The study will begin when the consented subject starts a new therapy, either an oral targeted agent (pazopanib, sunitinib, axitinib, cabozantinib, lenvatinib, everolimus) or infusional immunotherapy (nivolumab), and will continue for a duration of 48 weeks or until drug is permanently discontinued by their primary oncologist. All study subjects will be asked to log their symptoms through Carevive software weekly for 12 weeks and then every other week for the next 36 weeks. Based on their symptoms, subjects will receive self-management instructions through the software (if applicable). Subjects will also be asked to monitor their medication compliance and health care utilization through the Carevive software once every four weeks for the length of the study. In addition, subjects will be asked to fill out a survey at their medical oncology office visits approximately every 3 months. This survey will include a distress assessment and a quality of life questionnaire. During these visits, a clinician will formally assess the subject's medication related adverse events. At the end of the study, the subject will be asked to fill out an in-office survey rating the usability of the Carevive software. On study completion, the subject's electronic medical record will be reviewed to determine health care utilization and oral targeted therapy refill history during the study period.

6.2 Screening and Recruitment

The study coordinator and investigators will review records to identify all active patients who meet eligibility criteria. Potential subjects will be approached for interest in participation at their next scheduled visit through the Genitourinary Medical Oncology Program at the Wilmot Cancer Center. After identification of potential subjects for the study, Drs. [name], [name] and [name], who are medical oncologist at the Wilmot Cancer Institute Genitourinary Oncology Program, will introduce the study to potential subjects.

6.3 Consent Process

For eligible subjects who are interested in study participation, the study coordinator or study staff member will come to the Wilmot Cancer Institute Genitourinary Oncology Clinic to review the informed consent process. The study coordinator or study staff member will walk the subjects through the consent form to ensure comprehension and the subjects will be given the option to sign the consent form. The study coordinator or study staff member will be available to answer any questions the subjects may have about any aspect of the study prior to consenting throughout the entire study period.

Subjects may choose to sign the informed consent immediately in the clinic or at a subsequent visit with the study coordinator or study staff after reviewing the informed consent at home and discussing it with others. Subjects must sign the consent and complete a baseline assessment prior to starting their new treatment with either oral targeted therapy or immunotherapy in order to remain eligible. The study coordinator is primarily responsible for obtaining all of the informed consents from study subjects; however the study staff PI, [name] and other co-investigators may obtain consents in cases where the study coordinator is not available. After completion of the consent process, the study team member will help the subject to schedule a baseline assessment which must occur within the two weeks prior to starting the new therapy.

If the subject does not wish to consent to the study, their reason for declining participation will be recorded in a deidentified manner via a screening log.

6.4 Baseline Assessment (Week 0)

The baseline assessment can occur on the day of consent if the subject is going to be started on treatment with either a new oral targeted agent or a new immunotherapy within the following two weeks. At this visit, the physician will perform a baseline toxicity check following the Common Terminology Criteria for Adverse Events (CTCAE) which will be documented in the subject's electronic medical record. Specifically, the following CTCAE parameters will be assessed: diarrhea, nausea, vomiting, fatigue, abdominal pain, rash, anorexia, weight loss, oral mucositis, cough and shortness of breath. The subject will be asked to fill out a demographics form, kidney cancer specific quality of life survey called the FKSI-DRS (Functional Assessment of Cancer Therapy-Kidney – Disease Related Symptoms) and to rank their distress using the NCCN (National Cancer Consortium Network) Distress Thermometer and Problem List for Patients on a tablet while in office. The subject will then log into the Carevive system on an office computer or tablet, provide their email address and complete an initial survey, which will assess their baseline symptoms using Patient Reported Outcomes Common Terminology Criteria for Adverse Events (PRO-CTCAE) questions for the following categories: diarrhea, nausea, vomiting, fatigue, hand/foot syndrome, rash, abdominal pain, anorexia, mouth sores, cough and shortness of breath.

6.5 Study Intervention - Carevive Assessments and Care plans (Week 1-12 and 14, 16, 18, 20, 22, 24, 26, 28, 30, 32, 34, 36, 38, 40, 42, 44, 46 and 48)

The initial survey will occur in office at the week 0 time point. Carevive will then email the subject a link to the survey weekly for the first 12 weeks and then every other week for 36 weeks, to complete 48 weeks or until the subject comes off of the study. This survey will consist of PRO-CTCAE adverse event questions. Subjects will then be provided with self-care management through this automated system. Self-care plans provide advice on managing the symptoms one is experiencing. For example, if the questionnaire indicates a subject is having “occasional” diarrhea, they will be instructed to try an over the counter anti-diarrheal, loperamide, and to keep a stool diary to identify any triggers. They will also be instructed to call the office if their bowel movements increase to 4 or more per day. If the diarrhea is instead rated as “frequently” or “almost constant” the subject will again be instructed to try loperamide but they will also be told to call their cancer care provider immediately, while also stressing the importance of hydration (drinking 8-10 glasses of water daily), and modifying the diet to avoid caffeine, alcohol, spicy foods and dairy.

Every four weeks the survey will also include questions about healthcare utilization and drug adherence. If a subject misses a login they will be sent a reminder the following week, if they miss two logins Carevive will notify our staff who will follow-up with them via telephone.

6.6 In-Office Assessments (Week 12, 24, 36 and 48)

Every 3-4 months at routine visits, the physician will perform a toxicity check and will document the grade of the following CTCAE parameters in the subject’s electronic medical record: diarrhea, nausea, vomiting, fatigue, abdominal pain, rash, anorexia, weight loss, oral mucositis, cough and shortness of breath. The subject will again be asked to fill out a FKS-DRS quality of life survey and the “NCCN Distress Thermometer and Problem List for Patients” on a tablet or computer while they are in the office.

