6.7 Final Assessment

At the 48 week timepoint, or when the subject withdraws from study, we will ask them to fill out the previously well-validated System Usability Scale (SUS) questionnaire on a tablet rating their experience with the Carevive software and care plans.

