15.0. DATA ANALYSIS AND MONITORING

15.1 Primary Outcomes:

Primary Aim 1: *To evaluate the feasibility and usability of symptom monitoring and management with Carevive software.* Specifically, we will determine the demand for this intervention by calculating the rate of compliance. For example, in the case of monthly compliance, the

proportion of subjects who log in at least once during this time frame will be reported. The threshold criteria for compliance based on previous studies [29-30], will be a monthly compliance of 75% (ie. during each month, an average of at least 75% of the subjects completed at least one Carevive survey). Compliance will be determined for both survey completion and access of generated care plans. A sample size of 50 subjects produces a two-sided 95% confidence interval with a width of 0.254 for a point estimate of 75% compliance. Separately patient-level compliance will be determined, based on the proportion of logins that the subject completed during the course of the study. Reasons for noncompliance will be elicited at their subsequent login and will be reported descriptively.

Patient-rated usability, based on their SUS survey results, will also be employed as a measure of feasibility. This survey will be administered to subjects at the end of the study. A Score of >68 indicates greater than average usability [25]. We will determine overall mean usability scores, and we can produce a 95% confidence interval for the mean with a width of 0.57 standard deviations, utilizing the sample of 50 subjects.

We will also determine potential implementation obstacles for Carevive software by asking patients who fail to consent to the study to provide their reasoning. This will be reported descriptively. We will also keep track of the proportion of patients who are approached who fail to consent.

15.2 Secondary Outcomes:

Primary Aim 2: *To determine how patient-reported toxicities correlate to the subject's quality of life, distress level, drug adherence, health care utilization and physician reported toxicities.* Grading of each symptom and numeric values for quality of life, distress level, drug adherence and health care utilization rate will be determined as described in the "Data Collection and Monitoring Section." The strength of the association between symptom grade and each outcome will be measured using the Spearman's rank correlation coefficient.

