Week		0	1	2	3	4	5	6	7	8	9	10	11	12	14	16	18	20	22	24	26	28	30	32	34	36	38	40	42	44	46	48	Treat ment D/C	
PR- Symptoms	PRO-CTCAE Carevive survey	X	X	X	X	X	X	X	X	X	X	X	X	X	X	X	X	X	X	X	X	X	X	X	X	X	X	X	X	X	X	X		
PR- Healthcare Utilization	Carevive survey 7s					X				X				X		X		X		X		X		X		X		X		X		X		
PR- Drug Adherence	Adherence 7s Carevive survey					X				X				X		X		X		X		X		X		X		X		X		X		
Software Utilization	Carevive collected data		X	X	X	X	X	X	X	X	X	X	X	X	X	X	X	X	X	X	X	X	X	X	X	X	X	X	X	X	X	X	X	
Care plan Utilization	Carevive collected data		X	X	X	X	X	X	X	X	X	X	X	X	X	X	X	X	X	X	X	X	X	X	X	X	X	X	X	X	X	X	X	
Consent Failure	Recorded on screening log	X																																
Quality of Life	FKSI-DRS in office	X												X					X							X						X		
Distress Score	Distress Thermomer in office	X												X					X							X						X		
Usability	SUS																															X	X	
CD- Symptoms	CTCAE	X												X					X							X						X		
CD- Healthcare Utilization	Electronic Medical Record																															X	X	
CD- Drug Adherence	Pharmacy Confirmed																															X	X	

Abbreviation: CD = Clinician Determined, PR = Patient Reported, PRO = Patient Reported Outcomes, CTCAE = Common Terminology Criteria for Adverse Events, FKSI-DRS = Functional Assessment of Cancer Therapy: Kidney Symptom Index- Disease related Symptoms, SUS = System Usability Scale

REFERENCES

1. National Cancer Institute. Bethesda, M., . *SEER Cancer Statistics Factsheets: Kidney and Renal Pelvis Cancer*. 2016.
2. National Cancer Institute. Bethesda, M., . *Kidney Cancer (adult) -- renal cell carcinoma*. . 2016, NCI.
3. Fellner, C., *Launch of Breakthrough Therapies Will Reshape Renal Cell Carcinoma Market*. P T, 2016. **41**(8): p. 523-5.
4. Hartmann, J.T. and C. Bokemeyer, *Chemotherapy for renal cell carcinoma*. Anticancer Res, 1999. **19**(2C): p. 1541-3.
5. Cella, D. and J.L. Beaumont, *Pazopanib in the treatment of advanced renal cell carcinoma*. Ther Adv Urol, 2016. **8**(1): p. 61-9.
6. Motzer, R.J., et al., *Overall survival in renal-cell carcinoma with pazopanib versus sunitinib*. N Engl J Med, 2014. **370**(18): p. 1769-70.
7. Klapper, J.A., et al., *High-dose interleukin-2 for the treatment of metastatic renal cell carcinoma : a retrospective analysis of response and survival in patients treated in the surgery branch at the National Cancer Institute between 1986 and 2006*. Cancer, 2008. **113**(2): p. 293-301.

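### No quality-of-life, distress or clinician toxicity assessment is scheduled when treatment stops, and the exit usability survey has no stated fallback for subjects who do not return

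*Combined protocol and SAP*

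**What the plan says.** **Length of participation.** Under 6.1 a subject is followed for 48 weeks, or until the oncologist stops the drug for good.

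**In-office measures.** FKSI-DRS, distress and clinician CTCAE are taken at baseline (6.4), which 6.3 requires before the new treatment starts. They are then repeated under 6.6, headed "In-Office Assessments (Week 12, 24, 36 and 48". The text of 6.6 gives a looser rule: "Every 3-4 months at routine visits, the physician will perform a toxicity check".

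**Schedule table.** The row labelled "FKSI-DRS in office" and the rows for the Distress Thermometer and CTCAE have no mark under Treatment D/C. That column is marked for software use, care-plan use, SUS, chart-based utilization and pharmacy-confirmed adherence. No other section adds the three missing instruments at discontinuation.

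**Usability.** Section 6.7 sets the SUS at week 48 "or when the subject withdraws from study, we will ask them to fill out the previously well-validated System Usability Scale", and 12.1.3 repeats that timing. Section 6.1 gives the setting: "the subject will be asked to fill out an in-office survey rating the usability of the Carevive software". Section 15.1 states the precision: "we can produce a 95% confidence interval for the mean with a width of 0.57 standard deviations, utilizing the sample of 50 subjects".

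**Analysis.** Section 15.2 plans Spearman correlations of symptom grade with quality of life, distress, adherence, health care utilization and physician-reported toxicity.

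**The concern.** Stopping treatment closes data collection, yet the schedule takes no quality-of-life, distress or clinician toxicity reading at that moment. Section 7.2 lists adverse events, severe concurrent illness and treatment change among the grounds for withdrawal. Subjects with heavy toxicity may therefore be over-represented among those without a reading near the stop. A correlation needs pairs: a home symptom score shortly before stopping has no matching quality-of-life, distress or clinician value. Section 15 does not say how such gaps are handled.

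The SUS raises a related but different issue. It is a measure under the primary aim, taken once, at exit. If subjects who leave early do not come back to the office, the mean rests on fewer people than planned, and possibly on a selected group.

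**Working it through.** **1. The plan's own figures.** Planned enrolment is 50 (3.1: "We expect to recruit 50 advanced renal cell carcinoma patients").

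- SUS mean, 95% interval width in SD units: 2 × t(0.975, n−1) / √n. For n = 50: 2 × 2.010 / 7.071 = 0.568, which agrees with the stated 0.57. This uses all 50 subjects.
- Compliance (15.1: "A sample size of 50 subjects produces a two-sided 95% confidence interval with a width of 0.254 for a point estimate of 75% compliance"): the exact Clopper-Pearson interval at 75% of 50 runs from 0.607 to 0.862, a width of 0.254. This also reproduces. It does not use the in-office instruments or the SUS.

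**2. What is collected around a stop.**

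| Data | At or near discontinuation | Source |
|---|---|---|
| FKSI-DRS, distress, CTCAE | Not scheduled | 6.6, schedule |
| PRO-CTCAE from home | Last survey due within 1–2 weeks | 6.5, schedule |
| SUS | Scheduled | 6.7, 12.1.3, schedule |
| Software and care-plan use | Scheduled | Schedule |
| Chart utilization, refill history | Taken at withdrawal | 12.3.5, 12.3.6 |
| Reason for withdrawal | Required on the CRF | 7.2 |

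**3. How old the last in-office value can be.** With visits at weeks 12, 24, 36 and 48, a subject who stops at week 13 has a value 1 week old (13 − 12). One who stops at week 23 has a value 11 weeks old (23 − 12). One who stops before week 12 has only the pre-treatment baseline. If visits are four-monthly, the spacing is 4 × 52/12 = 17.3 weeks, so baseline-only status lasts until about week 17.

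**4. Which correlations depend on it.** Of the five outcomes in 15.2, quality of life, distress and physician-reported toxicity come only from the in-office visit. Adherence and utilization also come from four-weekly home surveys and the medical record.

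**5. Illustrative size.** The documents give no discontinuation or non-return rate, so the values of n below 50 are assumptions.

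| n with data | SUS width (SD) | 95% interval for a correlation of 0.3 |
|---|---|---|
| 50 | 0.57 | 0.02 to 0.53 |
| 40 | 2 × 2.023 / 6.325 = 0.64 | −0.01 to 0.56 |
| 30 | 2 × 2.045 / 5.477 = 0.75 | −0.07 to 0.60 |

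The correlation column uses tanh(atanh(0.3) ± 1.96/√(n−3)). It treats 0.3 as an assumed value with one pair per subject; 15.2 does not say how repeated pairs are combined.

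Bias in mean SUS is the fraction missing times the difference between missing and observed subjects. For an assumed difference of 0.5 SD, 20% missing (n = 40) gives 0.2 × 0.5 = 0.10 SD, and 40% missing (n = 30) gives 0.4 × 0.5 = 0.20 SD.

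**The case against.** The strongest reply is that much of the story of an early stop is already captured. The withdrawal reason is mandatory, patient-reported symptoms arrive from home until exit, and refill and utilization data are pulled at withdrawal. The affected analyses are secondary and described as preliminary, in a single-arm feasibility study where 9.2 names respondent burden as a risk. This stands, and it limits the point to the quality-of-life, distress and clinician-grade readings. It does not remove the gap: a reason on a form is not a score and cannot be paired in a correlation.

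Several stronger readings are tempting but are not supported:

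- *That early stoppers leave no record of why they stopped.* Section 7.2 and the home surveys contradict this.
- *That the SUS leaves out early stoppers by design.* It is scheduled at withdrawal and marked under Treatment D/C. The risk is non-return. Only 6.1 places it in the office; 6.7 says it is done on a tablet, 12.1.3 gives no place, and 13.1 says self-reported questionnaires run in REDCap. Remote completion is unstated rather than excluded.
- *That everyone who stops before week 48 lacks a usable in-office value.* Some will have been seen a week or two earlier, and no discontinuation rate is given from which to count the rest.
- *That the looser visit rule halves the assessments.* Strict four-monthly visits fall at weeks 17.3, 34.7 and 52, so two come before week 48. But the heading of 6.6 fixes four visits, 6.1, 12.3.3 and 12.3.4 say about every three months, and week 48 has its own final contact. The two timings in 6.6 need reconciling; they do not establish a loss of half the data.
- *That the correlations are shown to be biased toward mild cases.* The documents do not say what share of stopping is due to toxicity. Informative missingness is plausible, not demonstrated.

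**Conclusion.** The point holds in a limited form. No FKSI-DRS, distress or clinician CTCAE reading is scheduled at discontinuation, although discontinuation ends participation. Three of the five correlations in 15.2 therefore have no paired value at stopping, and a subject who stops before the first post-baseline visit contributes no on-treatment pair to them. The loss is plausibly related to toxicity, but its size cannot be derived from the documents.

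For the SUS, the weakness is an in-office exit form with no stated fallback, set against a precision statement that needs all 50 responses. Under the assumed 40 or 30 responders, the width grows from 0.57 SD to 0.64 or 0.75 SD.

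The compliance criterion and its 0.254 width do not change. This is an inexpensive improvement that should be made, not a flaw that undermines the primary aim.

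**What to change.** 1. Mark FKSI-DRS, Distress Thermometer and CTCAE in the Treatment D/C column and name them in 6.7, at the same contact as the SUS.
2. State in 6.1 and 6.7 that SUS, FKSI-DRS and distress may be completed by REDCap link when the subject does not attend. REDCap is already the web-based system described in section 13. The link covers only the patient-completed forms, so a clinician CTCAE grade could still be missing for a subject who does not attend.
3. Reconcile the fixed weeks in the heading of 6.6 with the three- to four-monthly wording in its text.

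The cost is a change to the schedule table and a few sentences, a few extra minutes per subject at exit, and some remote rather than in-office completion.

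Two further additions are not needed. An extra PRO-CTCAE survey at discontinuation would largely repeat the home survey of the previous one or two weeks. An SUS at week 12, with the latest score used, would mix early and end-of-use ratings in one mean; that is a trade-off rather than a correction.

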12.3 Secondary Study Outcome Measures

12.3.1 Patient Reported Toxicities

Patient reported toxicity data will be collected via Carevive surveys weekly for the first 12 weeks and then every other week for another 36 weeks. The questions will be from the PRO-CTCAE which is a patient-reported outcome measure developed to evaluate the toxicities that clinical trial subjects experience [10]. We will not deliver the PRO-CTCAE in its entirety but will specifically ask about the following common toxicities that are experienced with oral targeted therapy and immunotherapy: diarrhea, nausea, vomiting, fatigue, hand/foot syndrome, rash, abdominal pain, anorexia, mouth sores, cough and shortness of breath.

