12.3.2 Clinician Reported Toxicities

Toxicities will also be formally assessed in-office every 3-4 months after commencement of a new targeted therapy/immunotherapy at routine follow-up visits. The clinician will assess several categories and rank them according to the CTCAE. The CTCAE are a set of criteria designed to standardize the adverse effects of cancer drugs for clinical trial purposes [26]. The categories chosen are common toxicities that occur with oral targeted therapy and immunotherapy: diarrhea, nausea, vomiting, fatigue, hand/foot syndrome, rash, abdominal pain, appetite, mouth sores, cough and shortness of breath

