Informatics for Integrating Biology and the Bedside (i2b2) will be used to help extract data from the electronic medical records. Specifically it will collect physician CTCAE ratings. The i2b2 clinical data query tool is made freely available to researchers at the University of Rochester (UR) through the leadership of the Clinical and Translational Science Institute (CTSI) and the UR Medical Center Information Systems Division. i2b2 is an open source informatics framework developed by the NIH-funded i2b2 Center at Harvard University to enable researchers to query clinical data from multiple clinical systems for research purposes. Through an easy-to-use graphical user interface, the i2b2 tool has the ability to perform a variety of queries for the purposes of cohort identification to support study feasibility, volunteer subject recruitment, and data visualization. Some examples of data currently available include patient demographics, diagnoses, medications, procedures, providers, laboratory results, microbiology results, patient questionnaires, and social history. De-identified data is available for study feasibility assessment and planning. With proper IRB approvals, users may

request identified data in the form of a user-specific i2b2 project, which can be exported for analysis.

The University of Rochester has developed a complementary tool to automate the process of moving clinical information from i2b2 to REDCap using an innovative graphical user interface. Researchers may use the tool to map clinical data in i2b2 to specific fields in a REDCap project using an application programming interface (API). With proper human subject approvals, identifiable information is available. Once in REDCap, information may be manipulated further, combined with other data collected outside the electronic health record system, and exported for analysis.

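### Sections 6.4 and 6.6 contradict 12.3.2 on whether clinicians grade hand/foot syndrome, which puts one of eleven patient-physician pairs in 15.2 at risk

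*Combined protocol and SAP*

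**What the plan says.** Four parts of the combined protocol and SAP bear on this.

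- **Visit procedures.** Section 6.4 (baseline) introduces a closed list for the physician: "Specifically, the following CTCAE parameters will be assessed: diarrhea, nausea, vomiting, fatigue, abdominal pain, rash, anorexia, weight loss, oral mucositis, cough and shortness of breath". Section 6.6 (weeks 12, 24, 36 and 48) repeats the same eleven terms, "diarrhea, nausea, vomiting, fatigue, abdominal pain, rash, anorexia, weight loss, oral mucositis, cough and shortness of breath", and has the physician chart a grade for each.
- **Clinician outcome definition.** Section 12.3.2 gives a different set of eleven: "diarrhea, nausea, vomiting, fatigue, hand/foot syndrome, rash, abdominal pain, appetite, mouth sores, cough and shortness of breath".
- **Patient-reported items.** Section 12.3.1 lists "diarrhea, nausea, vomiting, fatigue, hand/foot syndrome, rash, abdominal pain, anorexia, mouth sores, cough and shortness of breath". The same eleven appear at the end of 1.3 and in the patient part of 6.4.
- **Analysis and data source.** The aim in 15.2 relates patient-reported toxicities to several measures, ending with "drug adherence, health care utilization and physician reported toxicities". The method is one sentence: "The strength of the association between symptom grade and each outcome will be measured using the Spearman's rank correlation coefficient". On the i2b2 query of the medical record, 13.2 says: "Specifically it will collect physician CTCAE ratings".

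**The concern.** A patient-physician correlation for a symptom needs a grade from both sides. The lists that direct the physician at the visit leave out a symptom that patients are asked about throughout, and include one that patients are not asked about. If staff build the visit form from 6.4 and 6.6, there will be no physician grade for hand/foot syndrome. Weight loss will be graded with no patient item to set beside it.

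Two features make this worth settling early. First, the term matters for this population: 1.3 names hand/foot syndrome as common with sunitinib, with axitinib, and with cabozantinib and lenvatinib, all of which are study agents in 6.1. Second, physician grades are charted at the visit and extracted afterwards. A term that was never charted cannot be extracted, and the plan describes no step to reconstruct it.

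**Working it through.** There is no planned figure to reproduce. The check is a term-by-term comparison, followed by a count.

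**Inputs.** Patient list from 12.3.1; clinician lists from 6.4/6.6 and from 12.3.2; 50 subjects from 3.1; five clinician assessments from 6.4 (week 0) and 6.6 (weeks 12, 24, 36, 48).

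**Assumption on terms.** Oral mucositis (6.4/6.6) is taken as the partner of mouth sores, and appetite (12.3.2) as the partner of anorexia. The plan does not say so.

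| Symptom | Patient (12.3.1) | Clinician (6.4/6.6) | Clinician (12.3.2) |
|---|---|---|---|
| Diarrhea | yes | yes | yes |
| Nausea | yes | yes | yes |
| Vomiting | yes | yes | yes |
| Fatigue | yes | yes | yes |
| Rash | yes | yes | yes |
| Abdominal pain | yes | yes | yes |
| Cough | yes | yes | yes |
| Shortness of breath | yes | yes | yes |
| Anorexia | yes | yes | as appetite |
| Mouth sores | yes | as oral mucositis | yes |
| Hand/foot syndrome | yes | **no** | yes |
| Weight loss | no | **yes** | no |

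**Pairs available.**
- Under 6.4/6.6: 8 + anorexia + mouth sores = 10 of 11. Hand/foot syndrome is patient-only and weight loss is clinician-only.
- Under 12.3.2: 8 + anorexia + mouth sores + hand/foot syndrome = 11 of 11, with nothing left over on either side.
- If only identical words counted, the figures would be 9 of 11 under 6.4/6.6 (oral mucositis drops out) and 10 of 11 under 12.3.2 (appetite drops out). The difference between the two lists is one pair either way.

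**Ceiling on missing grades if 6.4/6.6 are followed.**
- All assessments: 50 × 5 = 250.
- On treatment only: 50 × 4 = 200, because the week 0 assessment precedes the new therapy (6.3, 6.4).
- Both assume that every subject attends every visit. Under 6.1 participation ends when the drug is permanently discontinued, and the plan gives no attrition rate, so no expected number can be derived.

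**Relevance by agent.** Section 6.1 lists six oral agents and nivolumab. Section 1.3 names hand/foot syndrome for four of these seven (sunitinib, axitinib, cabozantinib, lenvatinib) and does not name it for pazopanib, everolimus or nivolumab. It also names it for sorafenib, but 6.1 does not list sorafenib as a study agent, so that adds nothing here.

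**Does another section settle it?** No. The schedule table says only CTCAE, 14.0 says only that CTCAE results go in the chart, and 13.2 does not list the terms to be extracted. No section says which list prevails.

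**The case against.** A reader might infer that hand/foot syndrome will not be graded by clinicians, and that the comparison for it cannot be made. The documents do not support that. Section 12.3.2, which defines the clinician-reported outcome, names hand/foot syndrome among the categories the clinician will assess, and nothing ranks 6.4/6.6 above it. The loss depends on which section staff follow. Nor does anything show that the sponsor chose to leave the term out.

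Other points on that side also stand:

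- No clinician grade enters the primary outcome, which rests on survey and care-plan use, usability, and reasons for not taking part or not complying (2.2.1, 15.1).
- The patient-physician comparison is secondary and descriptive, with no threshold or decision attached. The correlation bullet in 2.3.1 does not mention physician-reported toxicities; they appear only in 15.2.
- Patient-reported hand/foot data are collected under either list, so their correlations with quality of life, distress, adherence and utilization remain possible.
- Section 15.2 does not spell out symptom-by-symptom pairing. It is the natural reading of a correlation based on symptom grade, but it is a reading.
- Section 1.3 names weight loss as a pazopanib effect, so recording it is not itself an error.

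These points limit the size of the problem but do not remove it. The contradiction is in the text, and the omission occurs identically in both visit sections, so staff working from either would have no prompt to chart the term.

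**Conclusion.** The plan is wrong as written: it is internally inconsistent, with moderate to low severity. Sections 6.4 and 6.6 cannot both be followed together with 12.3.2 on what the clinician grades. If the visit sections are followed, one of eleven patient-physician pairs is lost, with at most 250 hand/foot grades missing at 50 subjects, at most 200 of them on treatment, and fewer with attrition. If 12.3.2 is followed, nothing is lost. The count assumes symptom-by-symptom pairing in 15.2 and the two term matches set out in the table. How much information the lost pair would carry depends on the mix of drugs prescribed, which the plan does not give. The feasibility conclusion and the other ten pairs are not affected.

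**What to change.** Before data collection:

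1. Add hand/foot syndrome to the clinician CTCAE lists in 6.4 and 6.6, so that they cover every symptom in 12.3.2 and in the patient survey.
2. Name the same terms in the i2b2 extraction described in 13.2, and in whatever form clinicians use to chart the grades.
3. State in 15.2 that oral mucositis pairs with mouth sores and anorexia with appetite, preferably by using one set of terms throughout.
4. If weight loss is kept, label it clinician-only and outside the patient-physician pairs in 15.2, and say the same in 12.3.2.

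The cost is one added term in two lists, a sentence or two in 12.3.2 and 15.2, and one more graded item at assessments that already take place. No visit or patient questionnaire is added. The change concerns data capture only and touches no clinical management.
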